- Primary Outcomes (end points)

We identify five different constructs as primary outcomes for the program. According to the program's theory of change, we should observe effects in these different constructs in a sequential way. In particular, we expect that the program will bring about positive effects in some dimensions during the implementation of the 15-week program; for instance, in the maternal mental health and child rearing practices domains. Additionally, we expect that effects on other dimensions, such as early childhood development, will build up and become salient at the second follow-up assessment. For this reason, we will conduct two rounds of follow-up data collection that will take place one (1) month and twelve (12) months after the 15-week program has concluded, . This will enable us to observe the short and medium run impacts of the intervention.

The five primary outcomes and the hypothesis that guide this evaluation are:

- 1) Primary caregiver's mental health: Participation in the intervention arm of the evaluation will generate a reduction in the number of emotional symptoms reported by caregivers one month after the intervention has been completed (first follow-up) and one year after the end of the intervention (second follow-up)
- 2) Child rearing practices: Participation in the intervention arm of the evaluation will generate an increment in the number and type of reported child-rearing practices implemented by caregivers right after the end of the intervention (first follow-up). These effects will persist one year after the end of the intervention (second follow-up).
- 3) Healthy child-parent emotional bonds: Participation in the intervention arm of the evaluation will lower the stress in the child parent relationship (first follow-up) and will generate a positive effect in the quality of the attachment relationship between caregiver and children one year after the end of the intervention (second follow-up).
- 4) Children's mental health: Participation in the intervention arm of the evaluation will generate a positive effect in the caregivers' report of child mental health in the medium run; 12 months after the end of the intervention (second follow-up).

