- 5) Child's cognitive, social, and emotional development. Participation in the intervention arm of the evaluation will generate a positive effect in children's' cognitive and socioemotional development in the medium run; 12 months after the end of the intervention (second follow-up).

- Primary Outcomes (explanation)

Building upon the program's theory of change and evidence from the CPP clinical trials (Lieberman and Van Horn, 2011), we will observe caregivers and children's outcomes throughout two follow-ups after the end of the intervention. We will include reduced versions of instruments designed and adapted to address all five primary outcomes at each moment in the data collection (baseline, first and second follow-up). Nevertheless, we formulate differential hypotheses of the effect of the program on different constructs at different moments.

Below, we describe the schedule of data collection that we will implement for each cohort. We detail the psychometric scales and assessment instruments that will be included at each phase.

Baseline Assessment:

For each cohort, we will administer a detailed household survey prior to the start of the intervention. The survey includes nine different modules that aim to characterize subjects and their households according to the: (1) demographic composition of the household, (2) education attainment of the primary caregivers and head of the household, (3) labor participation and primary source of income for the household, (4) child composition of the household and basic health indicators, (5) parental locus of control, (6) reported household-level exposure to violence, (7) primary caregiver time-use; (8) living arrangements and physical conditions of the house, and (9) contact information for future assessment.

In addition, we will administer the following scales and instruments to assess the baseline level of our primary outcomes:

- 1) Primary caregiver's mental health: Measured with four sub-scales of the Symptom Checklist-90-R (Derogatis, 1994). This self-reported measure asks caregivers to report on several indicators of emotional well-being and mental health experienced during the last 30 days. In our evaluation, we focus on the sub-scales providing indicators for the extent of symptoms for the following psychopathologies: (i) Anxiety, (ii) Depression, (iii) Phobic Anxiety, and (iv) Interpersonal Sensitivity.

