- 2) Child rearing practices: Measured with a questionnaire in which caregivers report whether they engaged in any of the following six stimulating activities with their children in the previous week: (1) reading stories or looking at books with images; (2) telling stories; (3) singing songs; (4) playing with child; (5) taking the child outside; and (6) spending time in physical activities with child. To analyze this construct as a composite measure we will compute a summary score ranging from zero (no engagement in any activity) to six (engagement in the six activities), as previously done in several studies (e.g., Bornstein & Putnick, 2012; Cabrera et al., 2011; Jeong et al., 2017; Jeong et al., 2016; Sun et al., 2016).
- 3) Healthy child-parent emotional bonds: Measured with the parenting stress-index (PSI, Adibin, 2012), a measure focused on three major domains of stress: child characteristics, parent characteristics and situational/demographic life stress. We will analyze a composite measure of this scale and the individual sub-scales for the following domains: (i) parental distress, (ii) parent-child dysfunctional interaction, and (iii) difficult child.
- 4) Children's mental health: Measured with two separated scales reported by the caregiver. First, we will employ an adapted measure of the Trauma Symptom Checklist for Young Children (TSCYC, Briere, 2005) to describe child-levels of trauma and abuse-related symptomatology. Second, we will employ the brief version of the Infant Toddler Social Emotional Assessment (BITSEA, Carter & Briggs-Gowan, 2004) to screen for social, emotional, and behavioral problems in our population. For both scales, we will focus on composite scores, yet we will provide detailed findings for each subscale.
- 5) Children's cognitive, social, and emotional development: Measured at baseline with an adapted version of the Preschool Self-Regulatory Assessment (PSRA, Smith-Donald, Raver, Hayes & Richardson, 2007). This tool will provide independent scores of self-regulations in emotional, attentional, and behavioral domains. We will focus our report on a composite score, but also provide detailed findings for each subscale.

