Additionally, at baseline and the two follow-up assessments we will record child height and weight. With this information, we will construct height and weight z-scores for each age cohort, and compare with WHO international scales. These anthropometric measures, in addition, become an additional indicator of the children's development at baseline.

First Follow-Up: 1 month after end of intervention

For each cohort, we will re-assess all our participants in the aforementioned dimensions one month after the end of the treatment implementation. At this moment, we will also update key demographic and socioeconomic information to assess key socioeconomic changes. Following the program's theory of change, at this phase of the data collection, our primary outcomes include the primary caregiver's mental health, the caregiver's report of child rearing practices, and the caregiver's report of stress-index in parenting interactions (PSI, Adibin, 2012). We expect to observe positive effects at end line for the first two primary dimensions. For the latter, we may observe worse self-reported outcomes (higher levels of stress in the child-parent relation) in the treatment group relative to the control group. This, however would not be indicative of a negative effect of the intervention, but rather an improved understanding by the participants on the way in which trauma and adversities undermine the child-parent relationship.

Secondary outcomes at phase of data collection includes and observational measure of healthy child-parent emotional bonds, caregiver's reports of children's mental health (TSCYC and BITSEA), and direct assessment of social and emotional development of the child measured with the PSRA.

Second follow-up: 12 months after end of intervention

A year after the end of the implementation of the program for each cohort, we will again re-assess all our participants using the different scales and instruments described above to assess the key dimensions. Additionally, to better understand the change in the quality of the child-parent bond and children's cognitive and socioemotional development, we will also administer the following instruments.

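### Parenting stress at first follow-up: one section predicts a fall, another expects no benefit and rules in advance that a rise is not a negative effect

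*Protocol*

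**What the plan says.** All references are to the Protocol.

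- **Primary Outcomes (end points), hypothesis 3:** "Participation in the intervention arm of the evaluation will lower the stress in the child parent relationship (first follow-up"). The same hypothesis goes on to predict better attachment quality at one year.
- **Baseline Assessment, outcome 3**, gives the instrument: "Healthy child-parent emotional bonds: Measured with the parenting stress-index". A composite and three sub-scales are to be analysed: parental distress, parent-child dysfunctional interaction and difficult child.
- **First Follow-Up: 1 month after end of intervention** names three primary outcomes for that visit: caregiver mental health, child-rearing practices and the PSI. It continues: "We expect to observe positive effects at end line for the first two primary dimensions". On the PSI it says that "we may observe worse self-reported outcomes (higher levels of stress in the child-parent relation) in the treatment group relative to the control group", and then: "This, however would not be indicative of a negative effect of the intervention, but rather an improved understanding by the participants".
- **The same section** also plans an observer rating at this visit: "Secondary outcomes at phase of data collection includes and observational measure of healthy child-parent emotional bonds".
- **Second follow-up: 12 months after end of intervention** repeats the instruments: "we will again re-assess all our participants using the different scales and instruments described above to assess the key dimensions".
- **Minimum detectable effect size for main outcomes** specifies two-tailed tests throughout.

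**The concern.** There are two linked faults. First, a reader cannot tell what the trial predicted for the PSI one month after the programme. The hypothesis list says a fall. The visit schedule leaves the PSI out of the expected benefits and raises the possibility of an increase.

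Second, the sentence on a rise is written as a conclusion, with no criterion and no check. A two-tailed test can return a significant increase in parenting stress. Followed as written, the plan would read that result as better insight, without reference to planned data that might support or contradict that reading.

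The explanation is also applied in one direction only. Caregiver mental health, child-rearing practices and both child mental health scales are reported by the caregiver too. Changed perception is invoked to discount an unfavourable PSI result, but nowhere to qualify a favourable self-report.

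**Working it through.** The point rests on the text. The arithmetic only shows how large a rise the advance statement could cover.

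**Comparing the statements**

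| | Hypothesis 3 | First Follow-Up section |
|---|---|---|
| Construct | Child-parent emotional bond (stress) | Same |
| Measure | PSI (from Baseline Assessment) | PSI |
| Visit | First follow-up | First follow-up |
| Status | Primary | Primary |
| Expectation | Stress falls | Not among the expected benefits; may rise |
| Reading of a rise | Hypothesis fails | Not a negative effect |

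Hypothesis 3 does not name the PSI. The link comes from Baseline Assessment and First Follow-Up, where the PSI is the only stress measure given for this construct.

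Two passages might reconcile the statements, and neither does:

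- Primary Outcomes (explanation) says "we formulate differential hypotheses of the effect of the program on different constructs at different moments". Here the construct and the moment are the same.
- Secondary Outcomes lists the observed relationship, the two child mental health scales and the self-regulation assessment as secondary at first follow-up. The PSI is not on that list, so it stays primary.

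A fall would support hypothesis 3. A rise would fail it, yet is declared not negative. So no PSI result at this visit would be read as harm.

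**Smallest rise that would be significant**

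Inputs from the minimum detectable effect section: 18 centres (9 per arm), 1280 participants, ICC 0.04, two-sided alpha 0.05, power 80%, and a mention of covariates explaining 30% of outcome variability. Assumptions added here: equal centre sizes, outcome in total-SD units, 16 degrees of freedom (18 − 2), and the 30% applied at both levels.

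- No covariates: SE = √[4 × (0.04/18 + 0.96/1280)] = √[4 × (0.002222 + 0.000750)] = √0.01189 = 0.109.
- Threshold = t(0.975, 16) × SE = 2.120 × 0.109 = **0.231 SD**.
- With 30% explained: SE = √(0.7 × 0.01189) = 0.0912; threshold = 2.120 × 0.0912 = **0.193 SD**.

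Checking against the Protocol's own minimum detectable effects (0.262 and 0.2221): the multiplier is 2.120 + 0.865 = 2.985, which gives 2.985 × 0.109 = 0.325 and 2.985 × 0.0912 = 0.272. The stated figures are therefore not reproduced under these assumptions. Taking them at face value instead, threshold = MDES × 2.120/2.985 = 0.710 × MDES:

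- 0.710 × 0.262 = **0.186 SD**
- 0.710 × 0.2221 = **0.158 SD**

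The two bases are not compatible with each other, so the figures are best read as a range of 0.16 to 0.23 SD, labelled by source.

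**The case against.** The strongest reply is that the conflict is mild. The First Follow-Up section says stress may be higher; it does not predict it. Disclosing a possible reporting shift beforehand is more transparent than offering it after the results are known. The sentence sits in a data-collection schedule and is not a formal decision rule: the PSI remains primary, the test is unchanged, the estimate would be reported, and a rise would still fail hypothesis 3. The 12-month section also says that additional instruments, among them the observer rating, are meant to help understand change in the bond.

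All of that is accurate, and it limits the point to wording and interpretation. It does not remove it. A caveat would say that changed reporting is one possible explanation; this sentence says that a rise would not indicate a negative effect. The 12-month remark is general and is not tied to a PSI rise.

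Two objections to the remedy also deserve an answer. A non-directional PSI hypothesis would reconcile the sections too. Keeping hypothesis 3 is preferable because it is the formally listed hypothesis and two-sided testing already allows for either result. And the observer rating covers interaction quality, cognitive stimulation and emotional support, so it cannot show that higher parental distress is merely better insight. That is true: it can inform the explanation without settling it, which is another reason not to fix the conclusion in advance.

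**Conclusion.** The concern holds. The Protocol gives two different expectations for the same primary outcome, measure and visit, and fixes a benign reading of an adverse result with no check attached. The scope is one of the three primary outcomes at first follow-up, at one of two follow-up visits. No sample size, test or estimate changes. What changes is what the trial may conclude from a significant rise in parenting stress, which could be as small as 0.16 to 0.23 SD depending on the basis used. The finding depends on the text and not on those figures or the assumptions behind them. It should be corrected.

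**What to change.** 1. State one hypothesis for the PSI at first follow-up in both sections: keep hypothesis 3, tested two-sided, and say that a significant rise will be reported as an unfavourable result on that outcome.
2. Replace the sentence that rules out a negative effect with one saying that changed reporting is a possible explanation, to be examined against the observer-rated bond measure at first follow-up and the PSI at 12 months.
3. In Secondary Outcomes, make clear that the observer-rated result at first follow-up will be reported in either direction. The opening sentence there is neutral, but the reporting commitment that follows mentions only positive differences, and an unfavourable observer rating is the result that would count against the benign reading.

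The cost is wording only, since the data are already planned. The sponsor gives up a favourable reading written ahead of the result. The trial is listed as on-going, so the change should be dated to let readers see whether it preceded the first follow-up analysis.

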- 1) Healthy child-parent emotional bonds: Measured with an observation measured designed for this trial. This measure will describe the quality of the relationship between children and caregivers in the child-development center. An overall score will be produced and analyzed from observers' ratings to items targeting: (a) the quality of the interaction, (b) the cognitive stimulation provided in the situation, and (c) the emotional support provided during the situation.
- 1) Children's cognitive and social-emotional development: Measured with the international Development Learning Assessment (IDELA, Pisani, Borisova & Dowd, 2015). This direct assessment tool, will describe the: (i) motor development, (ii) emergent language and literacy, (iii) emergent numeracy and problem solving, and (iv) socio-emotional skills of children.

Secondary Outcomes

Owing to the sequential follow-up design we have designed for these trial, we characterize unexpected differences in our child and relational outcomes at the first-follow up as secondary outcomes. As such, we postulate that positive differences in: (i) Quality emotional relationships

measured by observation of the interaction, (ii) child's mental health, measured with the TSCYC and BITSEA, and (iii) child's cognitive and socioemotional development, measured with the PSRA. While unpredicted according to our theory of change, positive differences could be observed at this phase of data collection. If present, we will report these findings as secondary outcomes.

- **Experimental Design (Public)**

- Experimental Design Details

The experimental evaluation of *Semillas de Apego* will be conducted as a Cluster-Randomized Control Trial (C-RCT). The eligible population for the study are all families served by Genesis Foundation's ECDC in Tumaco, Colombia and whose children's ages range between 2 to 4 years of age. For example, for the first cohort, the children should have been born between August 1st, 2014 to April 1st, 2016.

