- 40 groups of 16 participants in treatment and 640 participants in the control arm. (n = 1280)

- **Minimum detectable effect size for main outcomes (accounting for sample design and clustering)**

With 1280 participating households, nested in 18 child development centers, half of which are randomly assigned to an implementation cohort of the program, we estimate to have 80% of power to detect effect sizes ranging from 0.262 to 0.2221 at minimum. This range of minimal detectable effect sizes (MDES), is based on estimates in which we define a 0.05 probability of type I error, assign 9 clusters and half of the individual-level sample (640) to the treatment, and employing two-tailed tests in all our estimations. For all our estimations, we assume an Intra-class correlation coefficient (ICC) of 0.04, based on pilot estimations and a review of the literature. All power calculations were conducted with Power-Up! (Dong & Maynard, 2013), and validated using EGAP's Online Power Calculation Tool.

The smaller estimated MDES assumes that no covariates will be used in the estimation models, which would account for 30% of outcome variability explained by demographic covariates. Considering the range of effect sizes observed in the pilot evaluation, we consider that this study is adequately powered to detect smaller effects sizes than those previously reported. Assuming an attrition rate of 8%, the effective sample, we still be powered to detect effect sizes of 0.27. Telephonic check-ups and small incentives will be used to minimize attrition.

Note: Security conditions have worsened in Tumaco, leading to some uncertainty regarding our ability to implement the program in 2019. In this extreme case, the trial would only be run over the two 2018 cohorts, with 640 participating households, nested in 18 child development centers, half of which are randomly assigned to an implementation cohort of the program. In such case, we estimate to have 80% of power to detect effect sizes ranging from 0.341 to 0.405 at minimum. This range of minimal detectable effect sizes (MDES), is based on the same estimates as above: 0.05 probability of type I error, 9 clusters and half of the individual-level sample (320) assigned to the treatment, two-tailed statistical tests in our estimations and an Intra-class correlation coefficient (ICC) of 0.04. If we account for covariates, and assuming an attrition rate of 8%, we be powered to detect effect sizes of 0.404.

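### Reporting of the four one-month secondary measures is tied to favourable differences being present, although the same measures are listed elsewhere without condition

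*Protocol*

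**What the plan says.** Two sections of the protocol deal with the secondary outcomes at the one-month visit.

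- **First Follow-Up (1 month after end of intervention)** defines them by instrument: "Secondary outcomes at phase of data collection includes and observational measure of healthy child-parent emotional bonds", followed by the caregiver-reported TSCYC and BITSEA and the directly assessed PSRA. No condition on the result is attached.
- **Secondary Outcomes** defines them by result: "we characterize unexpected differences in our child and relational outcomes at the first-follow up as secondary outcomes". It lists the same measures: the bond and the two symptom scales appear as "measured by observation of the interaction, (ii) child's mental health, measured with the TSCYC and BITSEA". The PSRA is the third item of that list. It then says that, although the theory of change does not predict them, "positive differences could be observed at this phase of data collection. If present, we will report these findings as secondary outcomes".

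One other place touches on reporting. Under **Baseline Assessment**, the protocol says of TSCYC and BITSEA: "For both scales, we will focus on composite scores, yet we will provide detailed findings for each subscale". The PSRA item there has a similar sentence, but it introduces the PSRA as a baseline measurement. Neither sentence covers the observed bond measure.

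**The concern.** A secondary outcome should be fixed by what is measured and when, not by what is found. The Secondary Outcomes section makes membership of the category, and the promise to report, depend on a favourable difference appearing. It does not say that other results will be withheld. But the only reporting sentence specific to these measures at this visit is the conditional one, and it has no counterpart for null or unfavourable results.

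If that section governs rather than the First Follow-Up list, two things follow. The one-month estimates that reach the reader are selected for being favourable and so are too large on average. And a one-month worsening in trauma symptoms, behaviour problems or self-regulation could be left out with no departure from the protocol. An unfavourable early result is not far-fetched: the protocol itself foresees that the parenting stress index may look worse in the treated arm at one month. That index is primary at this visit and is outside the wording at issue.

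**Working it through.** **Text comparison**

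| | First Follow-Up section | Secondary Outcomes section |
|---|---|---|
| Measures | Observed bond, TSCYC, BITSEA, PSRA | The same four |
| Defined by | Instrument and visit | Whether a difference appears |
| Favourable result | Listed as an outcome | Will be reported |
| Null result | Listed as an outcome | No commitment |
| Adverse result | Listed as an outcome | No commitment |

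The statement that instruments for all five constructs are used at every wave commits to collection, not to reporting.

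**Size, as an illustration**

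The protocol gives no figure on this point to reproduce. The inputs below come from its minimum detectable effect section: 18 centres (9 per arm), 1280 participants in equal halves, two-sided 0.05, and "we assume an Intra-class correlation coefficient (ICC) of 0.04". The printed minimum detectable effects are not used. Outcomes are in SD units, and positive means favourable.

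1. Standard error of the treatment difference, without covariates:
 SE = √[4 × (0.04/18 + 0.96/1280)] = √[4 × (0.002222 + 0.000750)] = √0.011889 = 0.109 SD.
 If covariates explain 30% of the variance at both levels (the 30% is the protocol's; applying it at both levels is an assumption): 0.109 × √0.7 = 0.091 SD.

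2. Chance, with no true effect, that at least one of the four is significant and favourable:
 - independent measures: 1 − 0.975⁴ = 9.6%
 - all pairs correlated 0.5 (assumed; multivariate normal): 7.8%
 - all pairs correlated 0.7 (assumed; multivariate normal): 6.5%

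3. Average size of a null estimate reported because it was significant and favourable:
 - z test: the mean of a standard normal above 1.96 is 2.338, so 2.338 × 0.109 = 0.255 SD, or 2.338 × 0.0912 = 0.213 SD.
 - t test on 16 df (18 centres − 2) with estimated SE: with c = 2.120, the mean in SE units is (1 + c²/16)⁻⁸ / √(2π) / 0.025 = 1.2809⁻⁸ × 0.3989 / 0.025 ≈ 2.20. So 2.20 × 0.109 = 0.240 SD, or 2.20 × 0.0912 = 0.201 SD. Simulation with 8 million draws gives the same values.

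4. If a difference counts as present on sign alone: the average null estimate is √(2/π) × SE = 0.798 × 0.109 = 0.087 SD, or 0.798 × 0.0912 = 0.073 SD. With four independent measures, at least one would have a favourable sign 1 − 0.5⁴ = 93.8% of the time.

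5. If the true effect were a worsening of 0.20 SD (assumed): P(estimate ≤ 0) = Φ(0.20/0.109) = 0.967, or Φ(0.20/0.0912) = 0.986. In 97% to 99% of such trials the result falls where the Secondary Outcomes section promises nothing.

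**The case against.** The strongest reply is that the Secondary Outcomes section is a labelling rule. It follows from the sequential design and calls early effects unpredicted. On this view it promises only that such effects will be called secondary and not promoted to primary, which is a conservative step. Its opening phrase has no direction, and the paragraph is grammatically broken, so a strict rule should not be read into it. This reading is possible. It does not remove the condition: the text goes on to narrow to positive differences and makes reporting hang on their presence, and even the undirected phrase leaves out null results.

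Second, the protocol has no sentence promising to report regardless of direction for any outcome; naming a measure at a visit is how it commits. That is fair, and the First Follow-Up list alone would then be enough. The defect is that a second section attaches a condition to these four measures which no other outcome carries.

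Third, the Baseline Assessment wording on subscale findings may be meant for every wave, since scoring rules for outcomes that are primary at follow-up also sit there. Even so, it leaves out the observed bond measure. The statement that this measure's overall score will be analysed stands under the 12-month visit.

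Fourth, the observed bond measure is introduced as an addition at 12 months, so its collection at one month could be questioned. Both sections compared above place it at one month.

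Fifth, the 6.5% to 9.6% is ordinary multiplicity over four tests and would be the same under full reporting. That is correct. What full reporting changes is that the reader sees a chance finding beside the other three results.

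**Conclusion.** The concern holds. The protocol states a result-dependent reporting condition for four one-month secondary measures, and this conflicts with its own unconditional list. Whether anything would be withheld cannot be known from the text; the point is that the wording permits it.

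If selection were on significance, a null effect that reached the report would average about 0.20 to 0.24 SD (0.21 to 0.26 SD by z); if on sign alone, 0.07 to 0.09 SD. These sizes rest on the protocol's ICC and sample size, on the assumption that covariates act equally at both levels, and on the reading that reporting follows the condition. The correlations between measures and the 0.20 SD worsening are also assumed.

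The scope is limited. Type I error per test does not change, and the primary outcomes at one and 12 months, including the same child constructs at 12 months, carry no such condition. It should be corrected, but it does not threaten the primary inference.

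**What to change.** Reconcile the two sections by replacing the conditional sentence in Secondary Outcomes with, for example: *At first follow-up the observational bond measure, TSCYC, BITSEA and PSRA are secondary outcomes; estimates and two-sided confidence intervals will be reported for all of them regardless of direction or significance.*

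The remark that early effects on these measures are not predicted by the theory of change can stay as interpretation. The cost is one sentence. Both sections already place these measures at the one-month visit, so no data collection is added.
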